#### **7.1.2.7.3 Biospecimen and Data Repository**

Biospecimen banks are collections of stored human biological materials, assembled either through blood, urine, or surgical acquisition procedures, and which are linked to a database of de-identified patient information that can be associated with each sample. Patient information will be stored in RedCap. RedCap requires username, password and a 2-factor authentication. All personnel who have access to RedCap are HIPAA trained. All tissue, peripheral blood, urine, and stool samples collected will be labeled with a unique numeric identifier that will be coded for patient privacy protection before releasing specimens for processing. All de-identified specimens will be processed and stored at the UWMC GU Research Lab ([name]). The data and samples stored in this repository may be used by researchers and will be used for research purposes only and will not be sold.

#### **7.1.2.7.4 Tumor Infiltrating CD8+ T-Cell Density**

Post-treatment tumor infiltrating CD8+ T-cell density is a secondary endpoint in the trial. In pre- and post-treatment tumor tissue specimens CD8+ T-cell density will be examined by IHC performed on whole tissue histology sections. CD8+ T cell density will be assessed using a fluorescent tryamide-based immunohistochemistry (mIHC) approach to identify CD8 and tumor (pancytokeratin AE1/AE3). The assays will be performed on representative slides from formalin-fixed paraffin-embedded pre-treatment TURBT and post-treatment cystectomy tissue in the CLIA-regulated Integrated Clinical Trials Pathology Lab (ICTPL) at the Fred Hutchinson Cancer Center. Fluorescent whole-slide scanning will also be performed on the Aperio Versa (Leica). Digital images will be exported into Halo (Indica Labs) for quantitative image analysis of CD8+ T cell counts, CD8+ T cell density (CD8+/mm^2) as well as CD8+ T cell density at (within 50 microns) of the tumor-stroma interface.

#### **7.1.2.7.5 Multiplex Immunohistochemistry mIHC on tumor microarrays (TMAs)**

For additional exploratory analysis, tissue microarrays (TMAs) of pre- and post-treatment tumor tissues may be constructed using available tumor FFPE blocks. The TMAs will be constructed using three 1.0 mm diameter tumor core tissues containing at least 100 malignant cells representing the greatest extent of infiltration of lymphocytes. Also, a minimum of 20 (30 preferred) unstained 5-micron thick sections from both the pre- and post-treatment tumor samples will be cut into slides for additional correlative investigations. A 7-color mIHC will be performed using spectrally-resolvable fluorescent tryamides, followed by imaging and spectral deconvolution using the Vectra 3.0 slide scanner (Perkin-Elmer) as previously

described. Downstream analysis will be performed using Halo (Indica Labs). The mIHC panel will include the following analytes: (1) PD-1, (2) PD-L1, (3) CD8 (4) CD4 (5) CD66b (6) macrophage cocktail (CD68+CD163).

#### **7.1.2.7.6 Additional Analysis**

Other analysis that may be performed depending on resources, tissue quality and availability may include the following:

##### **Additional IHC Analyses**

As tissue availability permits, additional IHC and immunofluorescence (IF) staining is planned to further characterize functional immune phenotypes and targets of interest for future drug development. Utilizing the TMAs constructed from the pre- and post-treatment archived tumor specimens, additional mIHC stains planned, but not limited to the following: FOXP3, Ki-67, CTLA-4, Hsp27, PTEN, OX40, LAG3, TIM-3, KIR2DL, CSF1R, 4-1BB, IDO, GITR, TIGIT, CD27, CD73, CD40L, pSTAT1, RBP-J, CMAF, LGR4, LGR5, LGR6, SLAMF7, etc. Exact list of IHC biomarkers may be modified according to new target identification and emerging translational science. Immunoscore and immune reports may also be evaluated.

##### **Immune Gene Expression Analysis**

Baseline and post-treatment tumor cells will be isolated and enriched from patient tumor slides by macro-dissection. RNA will be extracted and assessed for quality control utilizing standard manufacturer RNA extraction kits and per manufacturer instructions. Extracted RNA from each sample passing quality control will be analyzed for the expression of immune mediating genes by standard quantitative PCR.

##### **Nanostring**

Nanostring-based transcriptional analysis will be performed on serial sections from the same FFPE specimens utilized for CD8+ T cell density measurements (see above). In brief, RNA will be extracted from unstained FFPE samples from microscope slides and transcripts of immunological interest will be quantified using the established panels from Nanostring using nCounter's Advance analyses technology. Up to 30 transcripts of particular interest for bladder cancer biology will be simultaneously measured using a custom "add-in" probe set.

##### **T-Cell Receptor Repertoire Analysis**

Pre- and post-treatment tumor cells will be isolated and enriched from patient pre- and post-treatment tumor slides by macro-dissection. DNA will be extracted and assessed for quality control utilizing standard manufacturer DNA extraction kits and per manufacturer instructions. Extracted DNA from each sample will be analyzed for T-cell and B-cell receptor mutations by next generation sequencing platform, statistical and bioinformatics analysis.

##### **RNASeq**

RNA from frozen pre- and post- treatment tissues will be isolated by the UW GU research laboratory and generated into RNASeq libraries through the Fred Hutch Genomics Core. Sequencing alignment and analysis will be conducted by the [name] Lab using standard

platforms including EdgeR and DESeq2.

### **Exome Sequencing**

Baseline tumor, post-treatment tumor, and germline DNA will be extracted from patient tissues (punches from FFPE or fresh frozen tissues). Extracted DNA from each sample will be analyzed for somatic mutations, copy number alterations, and mutational load estimate. Additional DNA based investigations on tumor DNA may be performed as tumor DNA availability and emerging analysis platforms permit.

## **7.1.2.8 Correlative Studies: Mandatory Peripheral Blood Samples and Analysis**

### **7.1.2.8.1 Peripheral Blood Assessments**

- **Before First and Second Neoadjuvant Pembrolizumab Dose**
  - Two 10 mL and two 5mL purple top tubes
  - One 10 mL Streck DNA tube
- **Pre-RC**
  - Two 10 mL and two 5mL purple top tubes
  - One 10 mL Streck DNA tube
- **Safety Follow Up Visit (after RC)**
  - Two 10 mL and two 5mL purple top tubes
  - One 10 mL Streck DNA tube
- **At time of recurrence, if feasible**
  - Two 10 mL and two 5mL purple top tubes
  - One 10 mL Streck DNA tube

### **7.1.2.8.2 Peripheral Blood Lymphocyte Subsets**

T-cell subset proportions (%CD4+ T-cells, %CD8+ T-cells, %Treg T-cells, %Myeloid Derived Suppressor Cells, %Natural Killer cells, etc.) will be determined by flow cytometry analysis.

### **7.1.2.8.3 ctDNA Analysis**

Cell-free ctDNA analysis will be performed on Streck DNA tube samples at time points of collection. Germline DNA can be extracted from “buffy coat”.

### **7.1.2.8.4 Cytokine Analysis**

The functional effects of study therapy will be analyzed by assessment of pre- and post-treatment plasma cytokine markers of interest (e.g. IFN- $\alpha$ , TGF- $\beta$ , IL-10, IL-4, IL-5, IL-13, IFN- $\gamma$ , etc.). The exact list of cytokines analyzed will be selected based on assay methodology optimization and validation testing. It is expected that a panel of a few biomarkers will be

analyzed to distinguish between major immune effector pathways. Additional exploratory analysis of the relationship between circulating free tumor DNA/RNA, micro-RNA, and other novel platforms will be pursued as resources and specimen availability permit.

### **7.1.2.9 Correlative Studies: Mandatory Urine Samples and Analysis**

#### **7.1.2.9.1 Urine Assessment and Sample Collection**

- **Before First and Second Neoadjuvant Pembrolizumab Dose**
- **Pre-RC**
- **Safety Follow Up Visit (after RC)**
- **At time of recurrence, if feasible**

Urine should be collected in standard analysis cup and 30mL aliquoted into two 15mL falcon tubes.

#### **7.1.2.9.2 Banking for Future Research: Urine Biomarker Analysis**

Urine samples will be banked and stored for future correlative work related to this study. Future analyses of urinary cytokine changes, urine cell pellet profiles, T-cell receptor repertoire, gene methylation and mutation analysis are proposed as resources and specimen availability permit. The exact list of urine biomarkers may be modified according to new target identification and emerging translational science. Stored samples will not be used for any studies unrelated to this trial.

### **7.1.2.10 Correlative Studies: Stool Sample Collection**

#### **7.1.2.10.1 Stool Assessment and Sample Collection**

- Before First and Second Neoadjuvant Pembrolizumab Dose
- At time of recurrence, if feasible

Two stool samples per time point should be collected in standard analysis tubes, one tube with 5 mL RNA later and one tube without preservative. Samples should be stored at -80 °C until analysis. **Plan to record the stool collection date.**

#### **7.1.2.10.2 Banking for Future Research**

Stool samples will be banked and stored. Future analyses will include microbiome diversity, metagenomic, and meta-transcriptomic evaluation and bacterial culturing depending on availability of resources. Stored samples will not be used for any studies unrelated to this trial.

### **7.1.2.11 Research Samples Processing**

All tissue, peripheral blood and urine samples collected will be labeled with a unique numeric identifier that will be coded for patient privacy protection. All specimens will be processed and stored at the GU Research Lab ([name]). Stored samples will not be used for any studies unrelated to this trial.

#### **7.1.2.11.1 Tissue Block or Slide Samples**

Tissue will be formalin-fixed and paraffin embedded (FFPE). Five- $\mu$ m sections will be cut and put on slides for H&E and IHC analysis. For frozen tissue processing (if 1 FFPE has been fulfilled), a cryomold will be pre-filled with OCT halfway, then the tissue will be placed in the middle of the OCT followed by filling the rest of the cryomold with OCT. The cryomold will be immediately put into an isopentane bath on dry ice for freezing. The frozen OCT-embedded tissue will be stored in -80°C. Stored samples will not be used for any studies unrelated to this trial.

#### **7.1.2.11.2 Peripheral Blood Samples**

Peripheral blood should be collected as noted above.

Two 5ml purple top will be sent to [name]'s lab for peripheral blood lymphocytes analysis.

Two 10ml purple top and 1 Streck DNA tube will be sent to the GU Research Lab ([name]) for processing.

#### **Purple Top Tubes Processing for Plasma and Buffy Coat**

**\*\*Process samples ideally within 120 minutes post-collection (record the blood draw time)\*\***

- Gently mix each blood sample by inversion 10 times (do not shake).
- Place tubes immediately on wet ice for five minutes
- Centrifuge at 1500 RPM for 15 minutes at 4°C.

After centrifugation, the plasma layer will be at the top half of the tube and the nucleated cells (WBC) will be in a whitish layer called the “buffy coat”, just under the plasma and above the red blood cells.

#### **Plasma Preparation**

- Using a transfer pipette for each tube take the top two-thirds of the plasma and transfer plasma into a 15-mL conical centrifuge tube, be careful not to disturb the buffy coat layer in each purple top tube (**NOTE:** see below for buffy coat

processing instructions).

- Transfer equal amounts of plasma from each tube into two labeled polypropylene tubes for cryopreservation.
- Store the two aliquots of plasma samples from each tube in a freezer at  $\leq -70^{\circ}\text{C}$  or colder. DO NOT ALLOW SAMPLES TO THAW.
- Stored samples will not be used for any studies unrelated to this trial.

### **Buffy Coat Preparation**

- From each purple top tube remove and aliquot the “buffy coat”; be careful not to disturb the layer of red blood cells.
- Store the aliquot of cells from each tube in one labeled polypropylene tube for cryopreservation.
- Store the samples in the freezer at  $\leq -70^{\circ}\text{C}$  or colder. DO NOT ALLOW SAMPLES TO THAW.
- Stored samples will not be used for any studies unrelated to this trial.

### **Streck Tube Processing**

Fill tube completely. IMMEDIATELY mix the blood sample by gentle inversion 8-10 times (do not shake). One inversion is a complete turn of the wrist (180 degrees and back). Store at ambient temperature ( $15\text{-}30^{\circ}\text{C}$ ). Stored samples will not be used for any studies unrelated to this trial.

#### **7.1.2.11.3 Urine Sample Processing**

Sites should collect urine samples as noted in Section 7.1.2.9.1

- Centrifuge the two 15 mL urine samples for 10 minutes at 3500 RPM.
- The supernatant from each tube should be transferred into three 5 mL labeled polypropylene tube for cryopreservation.
- The cell pellet from each tube should be re-suspended in 1 mL phosphate-buffered saline (PBS) and individually transferred into one labeled polypropylene tube. Centrifuge polypropylene tube at 3500 RPM for 10 minutes then aspirate the supernatant. The remaining cell pellet will be cryopreserved.
- Store the samples in the freezer at  $\leq -70^{\circ}\text{C}$  or colder. DO NOT ALLOW SAMPLES TO THAW.
- Stored samples will not be used for any studies unrelated to this trial.

### **7.1.3 Laboratory Procedures/Assessments**

Details regarding specific laboratory procedures/assessments to be performed in this trial are provided below. Laboratory tests for hematology, chemistry, urinalysis, and others are specified in Table 5.

**Neoadjuvant aMVAC+Pembrolizumab – non-UC MIBC Protocol**

Consortium Study No.: RG1006206

Version 8: 20-DEC-2023

**Table 5. Laboratory Tests**

Hematology	Chemistry*	Urinalysis	Other
Hematocrit	Albumin	Blood	Serum $\beta$ -human chorionic gonadotropin†
Hemoglobin	Alkaline phosphatase	Glucose	( $\beta$ -hCG)†
Platelet count	Alanine aminotransferase (ALT)	Protein	PT (INR)
WBC (total and differential)	Aspartate aminotransferase (AST)	Specific gravity	aPTT
Red Blood Cell Count	Blood Urea Nitrogen & Creatinine	Microscopic exam ( If abnormal )	Total triiodothyronine (T3)
Absolute Neutrophil Count	Carbon Dioxide ‡ (CO2 or bicarbonate)	results are noted	Free tyroxine (T4)
	Calcium	Urine pregnancy test †	Thyroid stimulating hormone (TSH)
	Chloride		Cortisol
	Glucose		Blood/urine/stool for correlative studies
	Potassium		
	Sodium		
	Total Bilirubin		
	Direct Bilirubin ( If total bilirubin is elevated above the upper limit of normal )		
	Total protein		

† Perform on women of childbearing potential only. If urine pregnancy results cannot be confirmed as negative, a serum pregnancy test will be required.

‡ If considered standard of care in the site region.

\*Phosphorus, Magnesium, LDH, Uric Acid, only as clinically indicated

Laboratory tests for screening should be performed within 10 days prior to the first dose of treatment. After Cycle 1, pre-dose laboratory procedures can be conducted up to 72 hours prior to dosing. Results must be reviewed by the Investigator or qualified designee and found to be acceptable prior to each dose of trial treatment.

#### **7.1.4 Other Procedures**

##### **7.1.4.1 Withdrawal/Discontinuation**

When a participant discontinues/withdraws prior to trial completion, all applicable activities scheduled for the final trial visit should be performed at the End of Treatment visit (which should be scheduled at earliest convenience per provider discretion, ideally within 4 weeks of discontinuation, if possible). Any adverse events which are present at the time of discontinuation/withdrawal should be followed in accordance with the safety requirements outlined in Section 7.2 - Assessing and Recording Adverse Events.

#### **7.1.5 Visit Requirements**

Visit requirements are outlined in Section 6.0 - Trial Flow Chart. Specific procedure-related details are provided above in Section 7.1 - Trial Procedures.

##### **7.1.5.1 Screening**

Screening is performed after attaining informed consent and within 12 weeks of diagnosis of MIBC by TURBT.

###### **7.1.5.1.1 Screening Period**

Screening should be completed as soon as possible and no later than 28 days from screening initiation.

###### **7.1.5.2 Treatment Period**

Treatment period is a 6-week neoadjuvant treatment after diagnosis of MIBC by TURBT and prior to RC. Treatment schedule will include aMVAC chemotherapy every 2 weeks (weeks 0, 2, 4, and 6) and pembrolizumab every 3 weeks (weeks 0, 3 and 6).

###### **7.1.5.3 Post-Treatment Visits**

Post treatment visits will follow standard of care guidelines per pathologic stage at time of RC.

###### **7.1.5.4 Safety Follow-Up Visit**

The mandatory Safety Follow-Up Visit should be conducted after RC or before the initiation of a new anti-cancer treatment, whichever comes first. All AEs that occur prior to the Safety Follow-Up Visit should be recorded. Participants with an AE of Grade > 1 will be followed until the resolution of the AE to Grade 0-1 or until the beginning of a new anti-cancer therapy,

whichever occurs first. Study treatment-related SAEs that occur after the last dose of treatment or before initiation of a new anti-cancer treatment should also be recorded, if known.

#### **7.1.5.5 Follow-up Visits**

Participants who discontinue study treatment for a reason other than disease progression will move into the Follow-Up Phase and should be assessed per standard of care. Every effort should be made to collect information regarding disease status until the start of new anti-cancer therapy, disease progression, death, end of the study.

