### 4.2 Secondary Objective(s)

(1) **Objective:** To assess the frequency and severity of toxicity according to Common Terminology Criteria for Adverse Events version 5.0 (CTCAE v5.0) in patients treated with aMVAC and pembrolizumab

(2) **Objective:** To evaluate the feasibility of neoadjuvant aMVAC and pembrolizumab as measured by the rate of patients able to receive RC within 10 weeks from completion of study therapy.

(3) **Objective:** To assess the recurrence-free survival (RFS), defined as time from trial enrollment to recurrence or death at the two-year time point in patients treated with aMVAC and pembrolizumab

(4) **Objective:** To assess the absolute and percentage (%) change in CD8+ TIL density at RC compared to pre-treatment TURBT

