## 5.2 Enrollment

Enrollment will be defined as the date participant starts treatment. Prior to this, while patient is being considered for the trial will be the screening period.

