#### **5.4.2 Prohibited Concomitant Medications**

Participants are prohibited from receiving the following therapies during the Screening and Treatment Phase of this trial:

- Antineoplastic systemic chemotherapy or biological therapy
- Immunotherapy not specified in this protocol
- Chemotherapy not specified in this protocol
- Investigational agents other than pembrolizumab
- Radiation therapy
- Live vaccines within 30 days prior to the first dose of study treatment and while participating in the study. Examples of live vaccines include, but are not limited to, the following: measles, mumps, rubella, a version of varicella/zoster, yellow fever, rabies, BCG, and typhoid vaccine. Seasonal influenza vaccines for injection are generally killed virus vaccines and are allowed; however, intranasal influenza vaccines (e.g., FluMist®) are live attenuated vaccines and are not allowed.
- Systemic glucocorticoids (> 10 mg of prednisone equivalent daily dose) for any purpose other than to modulate symptoms from an event of clinical interest of suspected immunologic etiology. The use of physiologic doses of corticosteroids are allowed. Standard use of steroids as premedication for cisplatin infusion is allowed with dose and duration at investigator discretion.

Participants who, in the assessment by the investigator, require the persistent use of any of the aforementioned treatments for clinical management should be removed from the study. All

treatments that the Investigator considers necessary for a participant's welfare may be administered at the discretion of the Investigator in keeping with the community standards of medical care. There are no prohibited therapies during the Post-Treatment Follow-up Phase.

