## **Neoadjuvant aMVAC+Pembrolizumab – non-UC MIBC Protocol**

Consortium Study No.: RG1006206  
Version 8: 20-DEC-2023

-Fresh frozen OCT (and extra fresh if possible): block/tissue to be collected and stored after FFPE (Stored samples will not be used for any studies unrelated to this trial.)

- 5 Research blood & urine, samples shall be obtained at time points noted below. (Stored samples will not be used for any studies unrelated to this trial.)  
Before first & second pembrolizumab dose, pre-radical cystectomy, post-op visit, and at the time of recurrence (if possible) - up to five time points  
-Peripheral blood: two 10 mL purple top tubes, two 5 mL purple top tubes, and one 10 mL Streck DNA tube  
-Urine: At least 30 mL in standard urine cup
- 6 Research stool samples shall be obtained before first & second pembrolizumab dose, and at the time of recurrence (if possible) - up to three time points (Stored samples will not be used for any studies unrelated to this trial.)
- 7 Radical cystectomy (RC) with bilateral (standard or extended) pelvic lymph node dissection to be performed as soon as deemed safe, and ideally within 10 weeks, after the last neoadjuvant infusion (RC is standard of care).
- 8 CT (or MRI as noted above) after final dose of study therapy and before surgery (standard of care)
- 9 If patient is removed from treatment for reason(s) other than progression, follow with regular tumor assessments as per standard of care until progression or start of new treatment. Adverse events should be reviewed at that post-RC safety visit, while phone follow-up may also be done as clinically needed to review potential subsequent adverse events; if those are felt to be at least possibly related to study therapy, they should be recorded as such.
- 10 Patients will be followed clinically and radiographically for at least 2 years post-cystectomy or when study-wide follow-up ends as per standard of care. First surveillance scan will be approximately 3 months after RC and then will continue every 3-6 months for 2 years as per treating physician and standard practice. Date of diagnosis for progression, first subsequent therapy and survival shall be reported. Phone follow-up may also be done for patients unable or unwilling to return for follow-up evaluations.
- 11 At time of recurrence, if feasible

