##### **7.1.1.5.3 Subsequent Anti-Cancer Therapy Status**

The Investigator or qualified designee will review all new anti-neoplastic therapy initiated after the last dose of trial treatment. If a participant initiates a new anti-cancer therapy after the last dose of trial treatment, the safety follow-up visit should ideally occur before the first dose of the new therapy. Once new anti-cancer therapy has been initiated the participant will move into survival follow-up.

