#### **End of Treatment and Follow-up Tumor Imaging**

In participants who discontinue study treatment prior to trial completion, tumor imaging should ideally be performed within 4 weeks or at the earliest convenience per provider discretion. If previous imaging was obtained within 4 weeks prior to the date of discontinuation, then imaging at treatment discontinuation is not mandatory.

In participants who discontinue study treatment without documented disease progression, every effort should be made to continue monitoring their disease status by tumor imaging using ideally the same imaging schedule used while on treatment to monitor disease status until the start of a new anticancer treatment, disease progression, pregnancy, death, withdrawal of consent, or the end of the study, whichever occurs first.

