#### **7.1.5.6 Survival Follow-up**

Participants who experience confirmed disease progression or start a new anticancer therapy, will move into the Survival Follow-Up Phase and should be contacted by telephone if needed to assess for survival status until death, withdrawal of consent, or the end of the trial, whichever occurs first.

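### The follow-up sections conflict on whether recurrence is collected after new anticancer therapy starts, and RFS events are not fully defined; 2-year RFS is likely, not certainly, too high if the stop rules are followed

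*Combined protocol and SAP*

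**What the plan says.** **Endpoint.** Secondary objective 3 (Section 4.2) reads: "To assess the recurrence-free survival (RFS), defined as time from trial enrollment to recurrence or death at the two-year time point". Section 5.2 sets the time origin: "Enrollment will be defined as the date participant starts treatment". The weeks before RC are therefore inside the RFS clock. Section 8.0 estimates time-to-event outcomes by Kaplan-Meier. It gives no censoring rule and no definition of recurrence.

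**Text that stops at new therapy.**
- Section 7.1.5.5, for patients who stop study treatment for a reason other than progression: "Every effort should be made to collect information regarding disease status until the start of new anti-cancer therapy".
- End of Treatment and Follow-up Tumor Imaging (within 7.1.2.6), for patients who stop without documented progression, imaging continues "until the start of a new anticancer treatment, disease progression, pregnancy, death, withdrawal of consent, or the end of the study, whichever occurs first".
- Flow-chart footnote 9, for patients taken off treatment for reasons other than progression, ends tumor assessments at progression or new treatment.
- Section 7.1.1.5.3, for any participant: "Once new anti-cancer therapy has been initiated the participant will move into survival follow-up". Section 7.1.5.6 says that patients who progress or "start a new anticancer therapy, will move into the Survival Follow-Up Phase and should be contacted by telephone if needed"; the stated purpose of the contact is survival status.

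**Text that does not stop.** Footnote 10 requires clinical and radiographic follow-up for at least 2 years after cystectomy, or until study-wide follow-up ends: "First surveillance scan will be approximately 3 months after RC and then will continue every 3-6 months for 2 years". It also asks for the dates of progression, first subsequent therapy and survival. The flow chart marks tumor imaging in the survival follow-up column.

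**Removal.** Section 5.4.2 says that patients who "require the persistent use of any of the aforementioned treatments for clinical management should be removed from the study". Section 5.5 speaks only of discontinuing study treatment.

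**The concern.** Site staff cannot follow both sets of instructions once a patient starts new therapy. If they follow the stop rules, a later recurrence is not recorded. The patient is then either censored at the start of therapy or carried as recurrence-free until death. Both matter if further therapy goes mainly to patients with residual disease, because the lost recurrences then fall mostly among patients without pCR. That would affect the 2-year RFS and also its relation to pCR and the biomarkers, which the exploratory objectives set out to describe.

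Patients who never reach RC are the least protected. Footnote 10 is written for the period after cystectomy, so these patients fall under footnote 9 and the end-of-treatment imaging text. The RFS definition names recurrence or death, and the plan does not say what happens to a patient who progresses before surgery and was never disease-free.

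**Working it through.** **The plan's own figure.** Section 8.0 says that binary proportions can be estimated to within 24% with 17 patients: 1.96 × √(0.25/17) = 23.8%. This agrees. One patient is 1/17 = 5.9 points. The documents give no RFS rate, no share starting further therapy and no share progressing before RC, so everything below rests on assumptions.

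**1. Censoring at new therapy.** Assumed: 36% have pCR (the design alternative in Section 8.0) with 2-year RFS of 85%. The other 64% average 50%, and half of them (32% of all patients) start further therapy at month 6. Event times are exponential in each group. Let a be the 2-year RFS of non-pCR patients without further therapy and b that of those with it, with a + b = 1.

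- True 2-year RFS = 0.36 × 0.85 + 0.32 × (a + b) = 0.306 + 0.320 = 62.6%.
- S(6) = 0.36 × 0.85^0.25 + 0.32 × a^0.25 + 0.32 × b^0.25, where 6 months is a quarter of 24.
- Large-sample Kaplan-Meier value = S(6) × (0.306 + 0.32a) / (0.36 × 0.85^0.25 + 0.32 × a^0.25).

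| a / b | S(6) | Ratio, months 6 to 24 | Kaplan-Meier | Shift (points) |
|---|---|---|---|---|
| 50% / 50% | 0.8838 | 0.4660/0.6148 = 0.7580 | 67.0% | +4.4 |
| 60% / 40% | 0.8818 | 0.4980/0.6273 = 0.7939 | 70.0% | +7.4 |
| 65% / 35% | 0.8791 | 0.5140/0.6330 = 0.8120 | 71.4% | +8.8 |
| 40% / 60% | 0.8818 | 0.4340/0.6002 = 0.7231 | 63.8% | +1.2 |
| 35% / 65% | 0.8791 | 0.4180/0.5918 = 0.7063 | 62.1% | -0.5 |

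The first row is upward even though therapy carries no extra risk within the non-pCR group, because everyone censored comes from that group. The shift vanishes or reverses only when treated non-pCR patients do clearly better than untreated ones.

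**2. No censoring, but only death counted after new therapy starts.** With recurrence hazard λ = -ln(b)/24 and hazard of death after recurrence μ = ln2/m, the share of the treated group whose recurrence is missed and who are still alive at month 24 is λe^(-24μ)[e^(24(μ-λ)) - e^(6(μ-λ))]/(μ-λ). Assume m is 12 to 18 months.
- b = 50%, m = 12: 0.2027, so RFS = 62.6% + 0.32 × 20.27% = 69.1%.
- b = 35%, m = 18: 0.2890, so RFS = 62.6% + 0.32 × 28.90% = 71.8%.
- b = 65%, m = 12: 0.1499, so RFS = 62.6% + 0.32 × 14.99% = 67.4%.

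Under this handling the shift (+4.8 to +9.2 points here) cannot be downward, because a recurrence is only delayed or missed.

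**3. Progression before RC.** If it counted only at death, with a fraction f progressing at month 3 and median survival m afterwards, RFS at month 24 would be too high by f × exp(-(ln2/m) × 21). For f = 5%, m = 12 this is 1.5 points; for f = 10%, m = 18 it is 4.5 points. This is the size of the ambiguity. The plan does not state that handling.

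**The case against.** The strongest reply is that recurrence data do not simply stop. Footnote 10 asks for scans and a progression date, the flow chart marks imaging in survival follow-up, and telephone contact is only for when it is needed. Section 7.1.5.5, the end-of-treatment imaging text and footnote 9 apply only to patients who stop treatment early without progression; patients who complete treatment and have RC come under footnote 10. This stands, and it makes the fault a contradiction rather than a uniform stop. It does not settle matters, because Sections 7.1.1.5.3 and 7.1.5.6 cover any participant and footnote 10 does not reach patients without RC.

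A reader might infer three stronger things that the documents do not support.
- That 2-year RFS is biased upward. No censoring rule is stated, adjuvant therapy is never described, and the direction depends on who starts further therapy.
- That pre-RC progression is excluded as an event. No passage says so; recurrence is undefined.
- That patients who progress are removed from the study and from the RFS denominator. Section 5.4.2 concerns persistent use of prohibited therapy in the Screening and Treatment Phase, and says nothing is prohibited afterwards. Progression is handled by Sections 5.5 and 7.1.5.6, which stop study treatment and move the patient to survival follow-up.

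It may also be said that captured deaths repair the estimate. They do so only for deaths inside the 2-year window; step 2 shows what remains otherwise. Finally, RFS is descriptive, has no decision rule, and carries an uncertainty of about 24 points either way. That limits the consequence, but imprecision does not excuse a systematic loss of events.

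**Conclusion.** The point holds as a conflict between follow-up instructions together with an incomplete endpoint definition. If the stop rules are followed and patients are censored at new therapy, 2-year RFS moves by roughly -0.5 to +9 points under the assumed inputs. If only deaths are counted after that point, the shift is upward. Overstatement is therefore likely but not established. Whether pre-RC progression counts is a separate gap, worth about 1.5 to 4.5 points if such patients counted only at death. All these sizes depend on assumed rates of RFS, further therapy, early progression and later survival. The primary pCR design and its decision rule are unaffected. The change should be made because it is cheap and because RFS is an outcome in every exploratory objective.

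**What to change.** 1. Amend Sections 7.1.1.5.3, 7.1.5.5 and 7.1.5.6, the end-of-treatment imaging text in 7.1.2.6 and footnote 9 to agree with footnote 10. Collect recurrence or progression dates from standard-of-care scans, and deaths, to 2 years for every treated patient, regardless of new therapy, treatment discontinuation or whether RC takes place.
2. In Section 8.0, state the RFS censoring rules, including that RFS is not censored at the start of new anticancer therapy.
3. In Section 4.2, objective 3, define recurrence, state that progression before or precluding RC is an RFS event, and say how patients without RC are handled.
4. Reconcile the removal wording in Section 5.4.2 with Section 5.5, so that outcome follow-up continues whatever is decided about treatment.

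The cost is protocol wording, some chart abstraction from scans already done as standard of care, and possibly a less favourable RFS estimate. No treatment, visit or sample size changes.
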